Procedure	Pre-screening	Visit 1 Screening		Visit 2 Baseline Day 0	Visit 3 Week 2 Day 14 ± 2 days	Visit 4 Week 4 Day 28 ± 2 days
Telephone Screening of Subjects	✓					
Informed Consent		✓				
Demographics, Medical History, Smoking Status		✓				
Current / Concomitant Medication		✓		✓	✓	✓
Oral Soft Tissue (OST) Examination		✓		✓		
Full Oral Hard Tissue (OHT) Examination		✓		✓		
Visual MLSI Stain Assessment		✓				
Inclusion / Exclusion Criteria		✓		✓		
Eligibility		✓		✓		
Brush Anterior Teeth for 30 Seconds with Tap Water Prior to Stain Assessment				✓	✓	✓
Pre-prophylaxis Full MLSI Stain Assessment of the Anterior Teeth ¹				✓		
Stratification / Randomisation				✓		
Dental Prophylaxis ²				✓		
Post-prophylaxis Visual MLSI Stain Assessment				✓		
Full MLSI Stain Assessment ¹					✓	✓
Dispense Study Dentifrice, Timer, Toothbrush and Diary/Instructions Card				✓		
Supervised Brushing on Site				✓ ³	✓	
Adverse Events				✓	✓	✓
Incidents				✓ ⁴	✓	✓
Subject Adherence and Continuance					✓	✓
Diary Compliance Check ⁵					✓	✓
Return Dentifrice, Toothbrush and Diary Card					✓	✓
Post Treatment Dental Prophylaxis						✓ ⁶
Study End						✓

Minimum 24 hours, up to a maximum of 2 weeks

1. Ten subjects will be randomly selected for repeat examinations across each assessment window (a total of 30 repeat examinations over the duration of the study).
2. AEs will be recorded from and including dental prophylaxis onwards.
3. Time of first brushing will be captured to distinguish dentifrice AEs from prophylaxis AEs.
4. Incidents will be collected from first use of the tooth brush, prior to stain assessment.
5. Time of each brushing occasion in addition to missed/additional brushings, and changes to smoking status will be captured in the subject diary.
6. Once all efficacy assessments have been completed randomised subjects who request so will be given a full dental prophylaxis, and will be recorded in the eCRF.

Document Name	207872 Clinical Protocol.doc		
Type	Version	Document Identifier	Effective Date
elido_clinical_doc	5.0; Most-Recent; Effective; CURRENT	090032d580d488e0	30-May-2017 04:37:09
Reason For Issue	Auto Issue		

PROTOCOL SYNOPSIS FOR STUDY 207872

Brief Summary

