- Review inclusion/exclusion criteria.
- Review of the oral care products the subject is currently using to confirm they do not contain any restricted ingredients.

Document Name	207872 Clinical Protocol.doc		
Type	Version	Document Identifier	Effective Date
elido_clinical_doc	5.0; Most-Recent; Effective; CURRENT	090032d580d488e0	30-May-2017 04:37:09
Reason For Issue	Auto Issue		

- Demographics, current/concomitant medications, medical history and smoking status captured.
- Oral examinations including an OST and a full OHT examination.
- Visual MLSI stain assessment of the facial (maxillary and mandibular) surfaces.
- Confirmation of subject eligibility.

Visit 2 - Baseline Visit

The following assessments will be conducted:

- Review of current/concomitant medications.
- Confirmation of subject eligibility and continuance.
- Full OST examination.
- Full OHT examination.
- Supervised brushing of the anterior teeth for 30 seconds using a wetted toothbrush.
- Pre-prophylaxis full MLSI stain assessment of the facial (maxillary and mandibular) and lingual (mandibular) surfaces.
- Stratification (based on total MLSI score of the facial surfaces only) and randomisation.
- Full professional dental prophylaxis.
- Post-prophylaxis visual MLSI stain assessment of the facial (maxillary and mandibular) and lingual (mandibular) surfaces to confirm overall MLSI = 0.
- Dispensation of study dentifrice, toothbrush, timer and diary/instructions card.
- Supervised brushing with subject's allocated dentifrice.
- AEs and Incidents following supervised brushing.

Visit 3 - Week 2

The following assessments will be conducted:

- Subjects return study dentifrice, toothbrush, and diary card to the clinical site.
- Review of current/concomitant medications, AEs and incidents.
- Review of completed diary to confirm timing of each brushing occasion in addition to missed/additional brushings, and potential changes to smoking status.
- Confirmation of subject adherence and continuance. Supervised brushing of the anterior teeth for 30 seconds using a wetted toothbrush.
- Full MLSI stain assessment of the facial (maxillary and mandibular) and lingual (mandibular) surfaces.
- Supervised brushing with subject's allocated dentifrice.
- AEs and Incidents following supervised brushing.

Document Name	207872 Clinical Protocol.doc		
Type	Version	Document Identifier	Effective Date
elido_clinical_doc	5.0; Most-Recent; Effective; CURRENT	090032d580d488e0	30-May-2017 04:37:09

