6.1.5. Oral Soft Tissue (OST) Examination

Where possible, this procedure should be conducted by a single trained dental examiner. The examination will be accomplished by direct observation and palpation with retraction aids as appropriate. The examiner will include examination of the Labial Mucosa (including lips), Buccal Mucosa, and Mucogingival folds, Gingival Mucosa, Hard Palate, Soft Palate, Tonsilar Area, Pharyngeal Area, Tongue, Sublingual Area, Submandibular Area and Salivary Glands. The results of the examination will be recorded in the eCRF as either normal or abnormal with details of any abnormalities. A brief description of any abnormality observed by the examiner or reported by the subject at the application site following dental prophylaxis or administration of the treatment dentifrices will be recorded as an AE.

An OST examination will be conducted at Visits 1 and 2, prior to any clinical assessments. While it is preferable to use the same OST examiner throughout the study, to facilitate subject flow, OST examinations may be carried out by different examiners.

Document Name	207872 Clinical Protocol.doc		
Type	Version	Document Identifier	Effective Date
elido_clinical_doc	5.0; Most-Recent; Effective; CURRENT	090032d580d488e0	30-May-2017 04:37:09
Reason For Issue	Auto Issue		

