6.2.4. Dental Prophylaxis

Randomised subjects will receive full mouth professional dental cleaning (using conventional prophylaxis paste), followed by flossing carried out by the hygienist, to remove all sub- and supra-gingival calculus, plaque and debris from the teeth, with particular focus on the anterior teeth. A second dental professional will confirm all sub- and supra-gingival calculus, visible stain (MLSI = 0), plaque and debris has been removed from the facial, palatal/lingual surfaces of the anterior teeth (visually and by tactile assessment using a dental explorer). If necessary, additional dental cleaning will be carried out to achieve this.

Dental prophylaxis may be carried out by different dental hygienists to facilitate subject flow.

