9.2.5. Criteria for Assessing Tolerability

The safety profile of the study treatments will be assessed with respect to adverse events (AEs) and oral soft tissue (OST) abnormalities.

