9.3.5. Safety Analyses

For the assessment of safety and tolerability, treatment emergent AEs will be summarised by treatment group. AEs and incidents will be listed. No inferential analyses will be performed to compare treatments with respect to safety data.

The safety profile of the study treatments will be assessed with respect to AEs. OST abnormalities are included as AEs if they appear or worsen after the initial assessment.

All safety data will be reported for the Safety population as per actual treatment received. All subjects screened will be included in the list of AEs.

All AEs will be reviewed by the Clinical Research Director or Designee prior to database freeze and will be coded using the Medical Dictionary for Regulatory Activities (MedDRA). During this review stage, AEs will be further categorised as oral or non-oral.

AEs will be regarded as treatment emergent if they occur on or after the start date and time of the first treatment usage (as determined by start date and time from the EXPOSURE/dispensing panel; if this date is missing a suitable alternative will be used eg date and time of randomisation). All other AEs prior to this will be considered non-treatment emergent.

The following summary tables and listings will be presented by treatment group.

- Table of treatment emergent AEs by Oral/Non-Oral and Preferred Term
- Table of treatment emergent AEs by SOC and Preferred Term
- Table of Treatment emergent treatment related AEs by Oral/Non-Oral and Preferred Term
- Table of treatment emergent treatment related AEs by SOC and Preferred Term
- Listing of all AEs (including Non-treatment emergent from All Subjects)
- Listing of SAEs
- Listing of incidents

In the event that there is nothing to report a null listing will be produced.

Document Name	207872 Clinical Protocol.doc		
Type	Version	Document Identifier	Effective Date
elido_clinical_doc	5.0; Most-Recent; Effective; CURRENT	090032d580d488e0	30-May-2017 04:37:09
Reason For Issue	Auto Issue		

No inferential analyses will be performed to compare treatments with respect to safety.

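### Prophylaxis AEs are only partly separated from dentifrice AEs: the example fallback time precedes prophylaxis, the Visit 2 lists show no AE check before brushing, and no field shown marks prophylaxis-related events

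*Protocol*

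**What the plan says.** **Aim.** Footnote 3 of the Schedule of Events, repeated in the SAP study schedule, states: "Time of first brushing will be captured to distinguish dentifrice AEs from prophylaxis AEs".

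**AE window.** Footnote 2 states: "AEs will be recorded from and including dental prophylaxis onwards". Protocol 7.2 opens collection at the same point. The Visit 2 lists in the synopsis and in Protocol 3.1 have one AE entry, placed last: "AEs and Incidents following supervised brushing".

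**Treatment-emergent rule.** Protocol 9.3.5 and SAP 4.7.1 compare AE onset with the recorded date and time of first use. Anything earlier is non-treatment emergent. For a missing value both say: "if this date is missing a suitable alternative will be used eg date and time of randomisation".

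**Order of procedures.** Protocol 6.2.4 says "Randomised subjects will receive full mouth professional dental cleaning", and the Visit 2 lists put randomisation before prophylaxis and prophylaxis before the first supervised brushing.

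**Soft tissue.** Protocol 9.2.5 says: "The safety profile of the study treatments will be assessed with respect to adverse events (AEs) and oral soft tissue (OST) abnormalities". Protocol 6.1.5 says: "An OST examination will be conducted at Visits 1 and 2, prior to any clinical assessments". No OST examination is scheduled at Visit 3 or Visit 4. Abnormalities observed or reported after prophylaxis or product use are recorded as AEs (6.1.5), and 9.3.5 brings OST findings into the safety analysis as AEs.

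**Causality.** Protocol 7.1.1 names dental prophylaxis in the AE definition. Protocol 7.3 requires each event to be assessed against study product. Template Listing 16.2.7.1 has one relatedness column, for study product.

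**The concern.** Every randomised subject has a full-mouth cleaning shortly before first using the study dentifrice, on the same day. Cleaning can itself produce oral soft-tissue complaints, and the protocol recognises this by setting out to tell the two sources apart. Clock time on Day 0 does most of that work. It fails if the substitute for a missing first-use time falls before the cleaning, and it weakens if nobody is scheduled to ask about AEs between cleaning and brushing. Timing cannot help at all with an event that the cleaning causes but that starts after brushing; only a causality field can identify that.

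At stake is the level of oral AEs shown for each dentifrice, including the two experimental ones. With no OST examination after treatment starts, the AE tables and listings carry the whole soft-tissue assessment.

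**Working it through.** No stated figure bears on this point, so the check is a trace of the Visit 2 order against the classification rule.

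**Inputs.** The order in the Protocol 3.1 Visit 2 list is: OST examination, water brushing, stain score, randomisation (time R), prophylaxis (P), post-prophylaxis stain check (S), dispensing (D), first supervised brushing (B), AE entry. Hence R < P < S < D < B. Let t be the AE onset. AE collection starts at P, so t ≥ P.

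**Rule with first-use time recorded.** Treatment emergent if t ≥ B.

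| Case | Onset | Result | Separated? |
|---|---|---|---|
| First-use time recorded | P ≤ t < B | Non-treatment emergent | Yes, by onset |
| First-use time recorded, cause is prophylaxis | t ≥ B | Treatment emergent, correct by timing | Only through the judgement on product relatedness |
| First-use time missing, R used | P ≤ t < B | Treatment emergent, since t ≥ P > R | No |

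With R as the cut-off, every AE in the collection window satisfies t > R, so the rule no longer separates anything for that subject.

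**A later cut-off.** Take any time F with P < F ≤ B, such as S or D.
- If t ≥ B, then t ≥ F. No AE starting at or after first use is dropped.
- If P ≤ t < F, the AE becomes non-treatment emergent, as footnote 3 intends.
- Only an AE in the short interval F ≤ t < B is still counted as treatment emergent.

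**AE entry at Visit 2.** Footnote 2 and 7.2 start collection at P, while the only AE entry in the Visit 2 lists comes after B. Classification uses onset, so an event elicited after brushing can still be given a pre-brushing onset. That onset then depends on the subject's recall, or on something noticed incidentally when the teeth are checked after cleaning.

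**Size.** Randomised per arm: 220/4 = 55. Evaluable per arm: 200/4 = 50.
- One misclassified subject: 1/55 = 1.8 percentage points, or 1/50 = 2.0.
- Three misclassified subjects: 3/55 = 5.5 points, or 3/50 = 6.0.

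The range of one to three subjects is an assumption for illustration. The documents give no frequency of prophylaxis AEs or of missing first-use times.

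**The case against.** The strongest reply is that the normal case works. First-brushing time is captured for this purpose, the rule uses time as well as date, and the AE listing template has a start-time column. First use is supervised on site, so the fallback should seldom be needed, and randomisation is offered only as an example of a substitute. All of this stands. A reader might infer that the AE rules cannot separate the two sources at all; the documents do not support that.

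A reader might also infer that a lesion first noticed after brushing must count as treatment emergent. It need not, because onset decides and not the moment of asking. What remains is weaker: the timing of the scheduled question makes a pre-brushing onset harder to establish.

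Treatment emergent is a statement about time, so a prophylaxis-caused event starting after brushing is correctly classed. Protocol 7.3 requires alternative causes to be considered, and Table 14.3.1.4 restricts to treatment-related events. It would therefore be too strong to say that only product causality is ever considered. For SAEs, 7.2 explicitly covers relatedness to procedures that the protocol requires. For ordinary oral AEs, however, nothing shown records prophylaxis as the cause. The eCRF is not among the documents, so this absence is inferred from 7.3 and the listing template.

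The lack of an OST display in the SAP text and templates might be read as a further gap. It is not pressed here. The list of displays in Attachment 1 is redacted, Protocol 6.1.5 says "The results of the examination will be recorded in the eCRF as either normal or abnormal with details of any abnormalities", and results from before treatment would not measure tolerability.

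Finally, safety is descriptive, and using randomisation time over-counts treatment-emergent events rather than hiding them. That limits the importance of the point but does not remove the conflict with footnote 3.

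**Conclusion.** The point holds in a limited form. The onset rule does what footnote 3 promises when first-use time is recorded. It is unreliable in three places:

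1. The example fallback always precedes prophylaxis, so it reverses the intended classification of AEs that start before brushing. This should be rare.
2. The Visit 2 lists do not match footnote 2 and 7.2 on when AE collection begins. This does not require a missing first-use time, but it matters only if onset is misremembered or not noted.
3. A non-serious AE that prophylaxis causes and that starts after first brushing cannot be identified as such from any field shown.

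The effect is on the level of oral AEs reported within each arm and on small-count differences. Each misclassified subject adds about 1.8 points in an arm of 55. All arms have the same prophylaxis, so no bias between arms is expected, and efficacy is untouched. How many subjects would be affected cannot be derived from the documents. The correction is worth making because the AE data are the only route to soft-tissue tolerability and the changes are cheap.

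**What to change.** 1. **Fallback.** In Protocol 9.3.5 and SAP 4.7.1, replace the randomisation-time example with a Day 0 time after prophylaxis and no later than first brushing, such as dispensing or the post-prophylaxis stain check. As shown above, this cannot drop a dentifrice AE. The chosen time must be recorded. The named source for first use is the exposure/dispensing panel, so the stain-check time is the safer second choice if that whole panel is blank; the documents do not say whether it is captured.
2. **Visit 2 lists.** Reconcile the lists in the synopsis and Protocol 3.1 with footnote 2 and 7.2, so that AEs are asked about and recorded after prophylaxis and before the supervised brushing, as well as after it.
3. **Attribution.** Add a field for relatedness to dental prophylaxis to the AE record and to Listing 16.2.7.1. Count those events in a separate summary whatever their treatment-emergent status. Rows inside Tables 14.3.1.2 and 14.3.1.4 would not do, because both tables are limited to treatment-emergent AEs and so exclude events that start before brushing, which are the clearest prophylaxis cases.

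The cost is one extra AE question at Visit 2, one eCRF field, one listing column and a short count, with no added examination or visit. Attribution to prophylaxis would still rest on the investigator's judgement.

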10. STUDY GOVERNANCE CONSIDERATIONS

10.1. Posting of Information on Publicly Available Clinical Trials Registers

Study information from this protocol will be posted on publicly available clinical trial registers before enrollment of subjects begins.

10.2. Regulatory and Ethical Considerations, Including the Informed Consent

The study will be conducted in accordance with all applicable regulatory requirements, and with GSK policy.

The study will also be conducted in accordance with ICH Good Clinical Practice (GCP), all applicable subject privacy requirements, and the guiding principles of the current version of the Declaration of Helsinki. This includes, but is not limited to, the following:

- Before initiating a trial, the investigator should have written and dated approval/favourable opinion from the IEC for the trial protocol (including amendments), written informed consent form, consent form updates, subject recruitment procedures (e.g., advertisements), safety statement (including any updates) and any other written information to be provided to subjects. A letter or certificate of approval will be sent by the investigator to the sponsor prior to initiation of the study, and also when subsequent amendments to the protocol are made.
- Signed informed consent to be obtained for each subject before participation in the study (and for amendments as applicable)
- Investigator reporting requirements (e.g. reporting of AEs/SAEs/protocol deviations to IEC)
- GSK will provide full details of the above procedures, either verbally, in writing, or both.

10.3. Quality Control (Study Monitoring)

In accordance with applicable regulations including GCP, and GSK procedures, the study monitor will contact the site prior to the start of the study to review with the site

Document Name	207872 Clinical Protocol.doc		
Type	Version	Document Identifier	Effective Date
e1do_clinical_doc	5.0; Most-Recent; Effective; CURRENT	090032d580d488e0	30-May-2017 04:37:09
Reason For Issue	Auto Issue		

staff the protocol, study requirements, and their responsibilities to satisfy regulatory, ethical, and GSK requirements.

When reviewing data collection procedures, the discussion will include identification, agreement and documentation of data items for which the eCRF will serve as the source document.

The study monitor will monitor the study and site activity to verify that the:

- Data are authentic, accurate, and complete.
- Safety and rights of subjects are being protected.
- Study is conducted in accordance with the currently approved protocol and any other study agreements, GCP, and all applicable regulatory requirements.

The extent and nature of monitoring will be described in a written monitoring plan on file at GSKCH. The investigator (or designee) agrees to allow the monitor direct access to all relevant documents and agrees to co-operate with the monitor to ensure that any problems detected in the course of these monitoring visits are resolved.

10.4. Quality Assurance

To ensure compliance with GCP and all applicable regulatory requirements, GSK may conduct a quality assurance assessment and/or audit of the site records, and the regulatory agencies may conduct a regulatory inspection at any time during or after completion of the study.

In the event of an assessment, audit or inspection, the investigator (and institution) must agree to grant the advisor(s), auditor(s) and inspector(s) direct access to all relevant documents and to allocate their time and the time of their staff to discuss the conduct of the study, any findings/relevant issues and to implement any corrective and/or preventative actions to address any findings/issues identified.

The sponsor will be available to help investigators prepare for an inspection.

10.5. Conditions for Terminating the Study

Upon completion or premature discontinuation of the study, the study monitor will conduct site closure activities with the investigator or site staff, as appropriate, in accordance with applicable regulations including GCP and GSKCH Standard Operating Procedures (SOPs).

Document Name	207872 Clinical Protocol.doc		
Type	Version	Document Identifier	Effective Date
elido_clinical_doc	5.0; Most-Recent; Effective; CURRENT	090032d580d488e0	30-May-2017 04:37:09
Reason For Issue	Auto Issue		

Both GSKCH and the Investigator reserve the right to temporarily suspend or prematurely discontinue this study at any time for reasons including, but not limited to, safety or ethical issues or severe non-compliance.

If the trial is prematurely terminated or suspended for any reason, the investigator site should promptly inform the trial subjects and should assure appropriate therapy/follow-up for the subjects.

In addition:

- If the investigator terminates or suspends a trial without prior agreement of GSKCH, the investigator site should promptly inform the sponsor and the IEC, and should provide the sponsor and the IEC a detailed written explanation of the termination or suspension.
- If the GSKCH terminates or suspends a trial, the investigator should promptly inform the IEC and provide the IEC a detailed written explanation of the termination or suspension.
- If the IEC terminates or suspends its approval/favourable opinion of a trial, the investigator should promptly notify the GSKCH and provide GSKCH with a detailed written explanation of the termination or suspension.

10.6. Records Retention

Following closure of the study, the investigator must maintain all site study records (except for those required by local regulations to be maintained elsewhere), in a safe and secure location.

The records (study/ site master file) must be maintained to allow easy and timely retrieval, when needed (e.g., for a GSK audit or regulatory inspection) and must be available for review in conjunction with assessment of the facility, supporting systems, and relevant site staff.

Where permitted by local laws/regulations or institutional policy, some or all of these records can be maintained in a format other than hard copy (e.g., microfiche, scanned, electronic); however, caution needs to be exercised before such action is taken.

The investigator must ensure that all reproductions are legible and are a true and accurate copy of the original and meet accessibility and retrieval standards, including re-generating a hard copy, if required. Furthermore, the investigator must ensure there is an acceptable back-up of these reproductions and that an acceptable quality control process exists for making these reproductions.

Document Name	207872 Clinical Protocol.doc		
Type	Version	Document Identifier	Effective Date
elido_clinical_doc	5.0; Most-Recent; Effective; CURRENT	090032d580d488e0	30-May-2017 04:37:09
Reason For Issue	Auto Issue		

The investigator must assure that the subject's anonymity will be maintained on eCRFs or other documents submitted to inVentiv Health, GSKCH, or any other GSKCH approved vendors. Subjects should not be identified by their names or initials, but by an identification code. The investigator should keep a separate log of subjects' codes, names and addresses. Documents not for submission to inVentiv Health, GSKCH, or any other GSKCH approved vendors, e.g. subjects' written consent forms, should be maintained by the investigator in strict confidence.

GSKCH will inform the investigator of the time period for retaining these records to comply with all applicable regulatory requirements (GSKCH recommends that documents be kept for 10 years). The investigator is also required to keep subject identification codes on file for at least 15 years after completion or discontinuation of the study. The minimum retention time will meet the strictest standard applicable to that site for the study, as dictated by any institutional requirements or local laws or regulations, GSKCH standards/procedures, and/or institutional requirements.

No study document should be destroyed without a prior written agreement between GSKCH and the investigator. The investigator must notify GSKCH of any changes in the archival arrangements, including, but not limited to, archival at an off-site facility or transfer of ownership of the records in the event the investigator is no longer associated with the site.

10.7. Provision of Study Results to Investigators, posting of Information on Publicly Available Clinical Trials Registers and Publication

Where required by applicable regulatory requirements, an investigator signatory will be identified for the approval of the clinical study report. The investigator will be provided reasonable access to statistical tables, figures, and relevant reports and will have the opportunity to review the complete study results at a GSK site or other mutually-agreeable location.

GSKCH will also provide the investigator with the full summary of the study results. The investigator is encouraged to share the summary results with the study subjects, as appropriate.

The procedures and timing for public disclosure of the results summary and for development of a manuscript for publication will be in accordance with GSK Policy.

Document Name	207872 Clinical Protocol.doc		
Type	Version	Document Identifier	Effective Date
elido_clinical_doc	5.0; Most-Recent; Effective; CURRENT	090032d580d488e0	30-May-2017 04:37:09
Reason For Issue		Auto Issue	

A manuscript will be progressed for publication in the scientific literature if the results provide important scientific or medical knowledge.

Document Name	207872 Clinical Protocol.doc		
Type	Version	Document Identifier	Effective Date
elido_clinical_doc	5.0; Most-Recent; Effective; CURRENT	090032d580d488e0	30-May-2017 04:37:09
Reason For Issue	Auto Issue		

